### 10.11. Procedure(s) to account for missing or spurious data

Reasons for being unable to collect data during an assessment will be recorded on the electronic case report form (eCRF), where appropriate. eCRFs will be assessed for missing data by ExeCTU and sites will be regularly chased for missing data. The ExeCTU will maintain a record of site compliance with eCRF completion. If data completion is poor, a triggered monitoring visit may be scheduled.

The eCRFs will include mandatory fields, which should be filled in before the eCRF can be saved to reduce the risk of missing data. Where questions may need to be left blank, options such as 'Not applicable' or 'Prefer not to say' will be available, to differentiate these from missing data. Validation rules will be set in to the REDCap database to check the entered data is in the expected data type and within an anticipated range. Manual queries will be raised on any data field where it is necessary to verify any discrepancies in the entered data, such as querying if the date of a visit does not correspond to the correct timepoint.

To reduce the risk of missing data for PROMs, participants will complete these during their (blinded) assessment visits, in between undergoing physical assessments. The local investigator will check for missing data as each PROM is completed.

# 10.12. Planned interim analysis and criteria for the premature termination of the trial

At the end of the first stage of this group sequential trial, a pre-specified interim analysis of the primary outcome (using O-Brien Fleming spending function for determination of boundaries) will be conducted to assess effectiveness and given sufficient evidence of activity of the drug, the trial will continue to the second stage. The single planned interim analysis will be undertaken after the first 100 randomised participants reach the primary endpoint (26 weeks post-randomisation). Full details of the interim analysis will be documented in the statistical analysis plan (or a separate interim analysis plan).

This interim analysis will also include a review of the pooled standard deviation of the change in absolute FVC between baseline and 26 weeks post-randomisation, with a blinded sample size re-estimation undertaken if indicated. If the observed pooled SD is larger than expected, implications on the required sample size will be discussed, taking into account other factors such as the emerging retention rate at the primary end point and rates of completeness of the primary outcome, and remedial action will be considered if deemed necessary.

This interim analysis is separate from the internal pilot phase (assessing trial progression over the first 12 months of participant recruitment (section 4.1)). The DMC will review the interim analyses and make a recommendation to the TSC regarding continuation of the trial.

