## 4.2. Main trial

Whilst the internal pilot phase aims to open a minimum of 15 sites, opening of the remaining (projected further 15) sites will continue throughout the latter period of the internal pilot phase. On progressing to the main trial period, additional sites may be sought if required, based on the observed recruitment rates during the internal pilot phase, to reach the overall recruitment target within the planned 25-month recruitment window.

There is a planned, separate, interim analysis after the first 100 participants reach the 26week primary endpoint, encompassing a review of the pooled standard deviation of the primary outcome (with opportunity for blinded sample size re-estimation if indicated) and a single interim analysis for effectiveness (see sample size and data analysis in section 10.1).

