#### **10. STATISTICS AND DATA ANALYSIS**

#### 10.1. Target sample size

The target is 222 randomised participants. The sample size calculation is based on a group sequential design with one interim analysis (i.e. total of two looks including the final analysis), using the O'Brien-Fleming spending function. The trial is powered at 90% to detect a between-group difference in change in absolute FVC between baseline and 26 weeks post-randomisation of 58ml, at the 5% two-sided significance level, conservatively assuming a standard deviation (SD) of change in absolute FVC between baseline and 26 weeks post-randomisation of 125ml and allowing for 10% loss-to-follow-up. The target difference is therefore equivalent to a standardised effect size of 0.464. This target difference was informed from data from the INBUILD trial as well as other published trials of fibrosing lung disease (CAPACITY, INPULSIS and ASCEND) [27-30]. The target difference was discussed and agreed with clinicians taking part in the trial and patient representatives. See Appendix 1 for power scenarios based on the planned recruitment target.

There is a planned review (at the time of the interim analysis) of the pooled standard deviation of change in absolute FVC between baseline and week 26, with a blinded sample size reestimation undertaken if indicated. If the observed pooled SD is larger than expected, implications on the required sample size will be discussed, taking into account other factors such as the emerging retention rate at the primary endpoint and rates of completeness of the primary outcome, and remedial action will be considered if deemed necessary.

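### Section 10.12 ties continuing the trial to evidence that the drug works, the opposite direction to the O'Brien-Fleming efficacy boundary it names

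*Protocol*

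**What the plan says.** Protocol section 10.12, whose heading covers premature termination, places a single interim analysis "after the first 100 randomised participants reach the primary endpoint (26 weeks post-randomisation". The analysis tests the primary outcome "using O-Brien Fleming spending function for determination of boundaries". The consequence is then stated in one clause: "given sufficient evidence of activity of the drug, the trial will continue to the second stage". No other sentence in the protocol links an interim result to stopping or continuing for effectiveness. Section 10.12 leaves the full details to the SAP or an interim analysis plan, and the DMC makes a recommendation to the TSC.

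The rest of the protocol describes an ordinary two-look efficacy design. Section 4.2 calls the look "a single interim analysis for effectiveness". Section 10.1 states: "The sample size calculation is based on a group sequential design with one interim analysis", with two looks in total counting the final analysis, "at the 5% two-sided significance level" and 90% power. Appendix 1 uses the same two-look basis. No futility or minimum-activity threshold appears in any of these places.

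**The concern.** In an efficacy group-sequential design, strong interim evidence is the reason a trial may stop early, and its absence is the reason to carry on to full size. The 90% power in section 10.1 depends on that: most of it comes from trials that miss the interim boundary and reject at the final analysis. Section 10.12 attaches continuation to positive evidence, which is how a go/no-go activity gate is worded. The only yardstick offered for that evidence is an efficacy boundary, and with fewer than half of the 222 participants contributing it is a demanding one.

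The sentence bears on whether the trial goes on after the first 100 participants. If its direction has to be corrected once unblinded interim results exist, the correction will look data-driven.

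**Working it through.** **Inputs (section 10.1 unless stated).** Difference 58 ml; SD 125 ml; two-sided alpha 0.05; power 90%; loss 10%; N = 222, 1:1; interim after 100 randomised reach week 26 (section 10.12).

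**Step 1. Reproduce the stated size.**
- Fixed design, per arm: 2 × (1.960 + 1.282)² × 125² / 58² = 97.6, so 98, or 196 in total.
- Two-look O'Brien-Fleming spending raises this to 196.2-196.8 evaluable. Dividing by 0.9 gives 218-219, close to the stated 222.
- 222 × 0.9 is about 200 evaluable, or 100 per arm, which is used below.

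**Step 2. Interim information.** The first 100 randomised give 45 evaluable per arm with 10% loss, or 50 with none. The information fraction t is 45/100 = 0.45 or 50/100 = 0.50.

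**Step 3. Interim boundary.** The O'Brien-Fleming-type spending function is 2[1 − Φ(z/√t)]. The protocol does not say how the two-sided alpha is spent, so both conventions are shown:
- A: 0.05 spent two-sided, z = 1.960.
- B: 0.025 spent in each tail, z = 2.241.

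**Step 4. Chance of crossing at the target effect.** E[Z1] = 58 / (125 × √(2/n1)), which is 2.20 for n1 = 45 and 2.32 for n1 = 50. P(cross) = 1 − Φ(c1 − E[Z1]). The observed difference needed to cross is c1 × 125 × √(2/n1).

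| Convention | n1 per arm | c1 | P(cross) | P(not cross) | Observed difference needed | Overall power, usual direction |
|---|---|---|---|---|---|---|
| A | 45 | 2.92 | 24% | 76% | 77 ml | 90.5% |
| A | 50 | 2.77 | 33% | 67% | 69 ml | 90.5% |
| B | 45 | 3.14 | 17% | 83% | 83 ml | 90.6% |
| B | 50 | 2.96 | 26% | 74% | 74 ml | 90.6% |

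The last column treats (Z1, Z2) as bivariate normal with correlation √t and E[Z2] = 58 / (125 × √(2/100)) = 3.28. In the usual direction the design delivers its stated 90% under either convention.

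**Step 5. Section 10.12 with the boundary as the meaning of sufficient evidence.** The trial continues only in the P(cross) column, so power cannot exceed 17-33%. Crossing needs an observed difference of 69-83 ml, more than the 58 ml target. The chance of crossing reaches one half only when the true effect equals that same 69-83 ml.

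**Step 6. Section 10.12 with activity as a separate, lower bar.** The efficacy boundary and the final critical value are kept, and the trial ends without rejection if Z1 falls below the bar.

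| Bar at interim | P(pass) at 58 ml | Overall power |
|---|---|---|
| Any observed benefit (Z1 > 0) | 98.6-99.0% | 90.1-90.4% |
| One-sided p < 0.2 (Z1 > 0.84) | 91-93% | 85.8-87.2% |

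These two bars are illustrations; the protocol gives none.

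**The case against.** The strongest reply is that the sentence is loose, not reversed. It does not say that the trial continues only if there is sufficient evidence, it does not say that the trial stops otherwise, and it does not equate activity with crossing the O'Brien-Fleming boundary. The outcome goes to the TSC as a DMC recommendation, so no statistic ends the trial automatically. A DMC that knows group-sequential designs would be unlikely to close a trial because an efficacy boundary was missed. Operating details are expressly left to other documents.

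Much of this stands. The 67-83% describes one reading of the sentence and is not a forecast of what will happen. Three stronger inferences should be resisted:

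- **That the stated 90% fails on any reading.** It does not. A bar of any observed benefit leaves power at about 90%.
- **That most trials of an effective drug would be lost, whatever the effect.** This holds at 58 ml. It ceases to hold once the true effect exceeds roughly 69-83 ml, depending on timing and spending convention.
- **That the DMC charter or the SAP repeats the error.** Neither is available, so nothing can be said about their content.

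What does not stand is that deferral cures the problem. A later document may add thresholds, but it should not have to reverse a direction that the protocol states. The lenient reading has its own difficulty: it needs a bar that appears nowhere and that section 10.1 does not mention, and it leaves the one boundary that is named without any consequence.

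**Conclusion.** The point holds as an error of direction and completeness in one sentence of section 10.12. The sentence links continuation to positive evidence, while the design in sections 4.2 and 10.1 and Appendix 1 calls for possible stopping when the boundary is crossed and continuation otherwise. Neither consequence is stated.

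Its size depends on the reading. With the efficacy boundary as the criterion, 17-33% of trials with the target effect would continue, and power is capped at that figure against the stated 90%. With a separate low bar, the loss ranges from essentially none to about four percentage points for the two bars tried, and it cannot be fixed without a threshold.

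The figures assume a 58 ml effect, SD 125 ml, 100 evaluable per arm at the end, 45-50 per arm at the interim, information proportional to evaluable numbers, and either two-sided spending convention. The sample size of 222 is not in question.

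**What to change.** Replace the sentence in section 10.12 with: If the interim test statistic crosses the O'Brien-Fleming efficacy boundary, the DMC may recommend stopping for efficacy; otherwise the trial continues to the planned sample size.

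If a futility or activity look is also intended, state it in a separate sentence as non-binding, with its own threshold, and report its effect on power alongside section 10.1. Check that the SAP or interim analysis plan and the DMC charter agree with the corrected wording.

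The cost is one sentence in the protocol and a consistency check of the related documents, done before any unblinded interim result exists. The sample size, the analysis model and data collection do not change.

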#### 10.13. Other statistical considerations

Any changes made to the SAP will be documented, including details of when the change was made (e.g. prior to data export).

#### **11. ECONOMIC EVALUATION**

A full within-trial cost-effectiveness analysis (CEA) will be conducted to estimate the incremental cost-effectiveness of the prednisolone intervention as compared to placebo.

Resources and costs of providing prednisolone will be established. Participant health, social care and broader societal resource use will be captured at baseline, 12 week and 26 week follow-up using a self-report resource use questionnaire (RUQ). The RUQ will be tailored for this participant population, with input from trial PPI representatives and the trial co-applicants [35]. Nationally recognised UK health and social care unit costs will be applied to the resource use data [36]. QALYs will be estimated using EQ-5D-5L data collected at baseline, 12 week and 26 week follow-up visits. The 'cross-walk' algorithm [35] will be used to provide QALY weights from the EQ-5D-3L UK general population valuation survey, in accordance with the current 'position statement' of the National Institute of Health and Care Excellence (NICE) [37].

Descriptive statistics will summarise costs and QALYs by the prednisolone and placebo groups. Longitudinal mixed effects linear regression models will be undertaken to test for differences in costs and QALYs. Models will adjust for the same baseline factors controlled for in the primary trial analysis, with appropriate random and/or fixed effects. In addition, the cost regression model will adjust for baseline costs, and the QALY model for baseline EQ-5D-5L values. The CEA will synthesise cost and outcome data to present incremental cost-effectiveness ratios for: i) the trial primary outcome, in the form of cost per change in FVC at 26 week follow-up, and ii) the policy relevant economic endpoint, cost-per-QALY at 26 week follow-up. Sampling uncertainty will be accounted for in the analysis, and we will explore the pattern and potential mechanisms of missing data in considering multiple imputation. Cost-effectiveness acceptability curves will be presented as appropriate using the net-benefit approach. These will show the probability that the prednisolone intervention is cost-effective (as compared to placebo) over a range of cost-per-QALY thresholds (e.g. the £20,000 and £30,000 thresholds considered by NICE). The CEA will initially be undertaken from a primary perspective of the NHS and Personal Social Services, with broader societal perspectives considered in sensitivity analyses, informed by input from the PPI representatives. A Health Economics Data Analysis Plan (HEAP) will be developed, which will be fully concordant with the SAP and the internationally recognised CHEERs guidelines for reporting CEA studies [38, 39].

#### **12. DATA MANAGEMENT**

#### 12.1. Data collection tools and source document identification

Local research teams will use the REDCap Clinical Data Management System (CDMS) provided by Exeter CTU to record participant data in accordance with the protocol. This CDMS will be the electronic CRF (eCRF). If direct data entry in REDCap is completed, this will be considered the source data, for example electronic PROMs and electronic consent forms. For data completed in participant medical records or on paper source data worksheets this will be considered the source data which is entered on the eCRFs in REDCap by the local research team.

The electronic randomisation and IMP management system is provided by Centre for Healthcare Randomised Trials (CHaRT; University of Aberdeen). The randomisation system will be integrated into CHORUS REDCap system and will not require a separate log in. IMP orders, receipt confirmation and individual pack statuses will be recorded directly in IMP-MS which is separate to the REDCap system and will require different login. IMP-MS must be kept up to date to ensure only available and non-expired drugs are able to be allocated by the system during randomisation. Sites will maintain local IMP accountability logs for the purposes of monitoring and inspection (full details in pharmacy manual). Data required for randomisation will be entered into REDCap directly. When the user confirms they are ready to randomise the necessary data will be piped into the CHaRT system which will automatically randomise, and the allocated pack ID will be piped back in to REDCap for the user to check (see section 12.3 for further details on data transfer between REDCap and CHaRT).

Sites will be required to answer data queries raised by ExeCTU in a timely manner within the trial database.

#### 12.2. Source data

At pre-screening and baseline assessment, the primary data source will be the medical notes and source data worksheets.

Participant questionnaires will be completed for PROMs at each timepoint listed below:

- Baseline
- Week 12 follow up
- Week 26 follow up

PROMs will be complete electronically in REDCap while the participant attends for their inperson visits. If any technical issues occur, or if the participant requests it, paper copies of the questionnaire can be used by the site team and the data transcribed into the database.

If completed electronically the trial database will form the source data, otherwise the paper questionnaire will form the source data.

The source data for the randomised allocation and the pack ID(s) allocated to the participant will be in the CHaRT randomisation system.

Medical case notes containing source data or other trial-related information should be identified by a label (or equivalent for electronic notes, where feasible), e.g. "Keep until at least dd/mm/yyyy" where the date given is at least fifteen years after the end of the trial.

#### 12.3. Data handling and record keeping

A Data Management Plan (DMP) will be created for the trial and will be updated throughout the trial as appropriate. Work instructions will be provided to the site teams on record keeping and data entry processes. Electronic systems will be validated, tested and documented before starting recruitment.

Any source data worksheets, paper questionnaires, paper consent forms and trial specific documents held by the site teams will be stored securely with access restricted and limited to research staff. If these are not stored in the ISF, a note to file will be placed in the ISF to indicate their location. Any source data recorded on paper questionnaires or source data worksheets will be transcribed into the eCRF.

Please see the data protection (section 15.5) for details on the electronic data capture system and how identifiable data will be stored.

#### 12.4. Access to data

Participants will be asked to consent to representatives of the Sponsor, the University of Exeter or regulatory agencies (e.g. MHRA) accessing their data that is relevant to their participation in the trial.

Access to the data held at participating sites will be restricted to those who have a relevant purpose to access the data. Access will be granted to authorised representatives from the Royal Devon University Healthcare NHS Foundation Trust as Sponsor, as well as representatives from University of Exeter and regulatory agencies e.g. MHRA, for the purposes of auditing, monitoring and inspection of the trial.

Data entered into the trial database (including unredacted uploads of paper consent forms and electronic consent forms) may be accessed by authorised members of the trial team at participating sites, ExeCTU and regulatory authorities (e.g. MHRA). Access to the database will be controlled by password protected individual user accounts. Delegated research staff will have access restricted by site, functionality and data that are appropriate for their location and role in the trial.

Exeter NIHR Clinical Research Facility at Royal Devon University Healthcare NHS Foundation Trust will be provided copies of participants informed consent forms to confirm the optional consent for research blood samples was provided.

Participants will also be asked to consent to data being shared with the following third-party providers:

- Centre for Healthcare Randomised Trials (CHaRT, University of Aberdeen) will provide the randomisation and IMP management system. CHaRT will not receive any identifiable information but will receive the participant's trial ID and eligibility criteria that are required for the randomisation. This system will also store the randomisation and IMP allocation data and a record of IMP pack statuses. Access to CHaRT's system will be restricted to password protected user accounts restricted by site, functionality and data appropriate to the user's role. Consent for this is required for a patient to participate in the trial.
- A company called Qureight Ltd will be provided copies of CT scans taken as standard of care, along with limited baseline demographic data. The CT scans and data will be pseudonymised with participant's trial ID. Consent for this is aspect of the trial is optional. An appropriate data sharing agreement will be put in place between the Sponsor and Qureight Ltd.

The above third parties will not be able to log into the trial database where the individual participant records are stored and the IMP manufacturer will not receive or hold any participant data.

#### 12.5. Archiving

ExeCTU will support sites to prepare trial records for archiving in accordance with the Data Management Plan. The Sponsor is responsible for arranging appropriate archiving of the Trial Master File and CDMS data on conclusion of the trial.

Essential documentation will be archived by each participating site as per local procedures, including the Investigator Site File, consent forms (including copies of electronic consent forms, where relevant) and any source data worksheets. The site must notify ExeCTU and the Sponsor of their archiving arrangements and the Sponsor must be granted access to the archived documents/data upon request.

The essential documentation will be archived for a minimum of 15 years after the end of the trial. After 15 years, all personal identifiable data will be securely destroyed upon authorisation from the Sponsor. The anonymised dataset, including the anonymised CT scans, will be stored indefinitely (see section 15.10).

#### 13. MONITORING, AUDIT & INSPECTION

A detailed monitoring plan will be agreed by the CI, ExeCTU and the Sponsor based on the trial risk assessment. The trial risk assessment and monitoring plan will be reviewed

periodically throughout the trial and updated as necessary (e.g. after amendments to the trial protocol).

Monitoring will be led by ExeCTU and will be conducted remotely, centrally and potentially onsite as required. This will include monitoring of unredacted consent forms; paper consent forms, where used, will be uploaded (unredacted) to the trial database for this purpose. Onsite monitoring may be conducted if triggered according to pre-defined criteria in the monitoring plan, or if concerns are raised by an individual with knowledge of the trial.

Sites will be expected to cooperate with monitoring procedures through timely provision of copies of requested documents and completion of self-audit checks where required. In the case of on-site monitoring visits, sites will be expected to provide space for the monitor(s) to work on the NHS Trust premises and provide access to all documents requested in the notification of monitoring visit letter. The PI or delegated member of the trial team must be available during on-site monitoring visits. The ExeCTU will provide sites with sufficient notice to prepare for a monitoring visit.

The Sponsor and/or regulatory authorities may audit or inspect the trial, including on-site visits at any time during the trial. All trial-related documents must be made available on request for monitoring and audit by the Sponsor or regulatory authorities.

The oversight committees will review data completeness, quality and accumulating safety data at agreed intervals throughout the trial.

